3.2 Adverse Event Reporting Requirements

The Adverse Event Reporting Requirements for all EAY131 subprotocols are outlined in the MATCH MASTER protocol. Please refer to those guidelines when determining if an event qualifies as a Serious Adverse Event (SAE) and requires expedited reporting via CTEP's Adverse Event Reporting System (CTEP-AERS).

In addition, the following section outlines agent specific requirements and must be followed to ensure all reporting requirements are met.

3.2.1 Additional instructions, requirements and exceptions for EAY131 – Subprotocol P

Additional Instructions

For instructions on how to specifically report events that result in persistent or significant disability/incapacity, congenital anomaly, or birth defect events via CTEP-AERS, please contact the AEMD Help Desk at [contact] or [contact]. This will need to be discussed on a case-by-case basis.

EAY131 – Subprotocol P specific expedited reporting requirements:

• Pregnancies: Pregnancies and suspected pregnancies (including a positive or inconclusive pregnancy test, regardless of age or disease state) occurring while the subject is on GSK2636771 or within 28 days of the subject's last dose of GSK2636771, are considered immediately reportable events. The pregnancy, suspected pregnancy, or positive/ inconclusive pregnancy test must be reported via CTEP-AERS within 24 hours of the Investigator's knowledge. Please refer to Appendix VIII in MATCH Master Protocol for detailed instructions on how to report the occurrence of a pregnancy as well as the outcome of all pregnancies.

EAY131 – Subprotocol P specific expedited reporting exceptions:

For Subprotocol P, the adverse events listed below **do not** require expedited reporting via CTEP-AERS:

 If an AE meets the reporting requirements of the protocol, and it is listed on the SPEER, it should *ONLY* be reported via CTEP-AERS if the grade being reported exceeds the grade listed in the parentheses next to the event.

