Reshaping the future of patient care

February 6, 2017

[name], MS RAC Head, Protocol and Information Office Quality Assurance Section CTEP, DCT, NCI [name]

Dear [name]:

Enclosed is Addendum #7 to EAY131-P, Molecular Analysis for Therapy Choice (MATCH): MATCH Treatment Subprotocol P: Phase II Study of PI3K Beta Specific Inhibitor, GSK2636771, in Patients with Tumors with PTEN Loss by IHC.

Please note, the following revisions to this subprotocol were not originally included in the submission of MATCH Addendum #7, which has since been reviewed by CTEP and the CIRB. Per discussions with PIO, changes to this subprotocol are now incorporated along with the resubmission of Addendum #7 to the CIRB. For any questions related to this submission plan, please contact [name] at PIO and/or [name] at the CIRB.

The following revisions to EAY131-P protocol have been made in this addendum:

	Section	Change	
1.	Cover Page	Updated Version Date and added "Addendum #7" to the activation date list	
2.	4.1	Footnote E: Updated language for additional specimen collection parameters under the Master Protocol. Table updated with additional optional blood submission time point.	
3.	5	Inserted "Investigator Brochure Availability" subsection, per CTEP request, for consistency across subprotocols.	
4.	Appendix I	Added additional instructions to pill calendar directions for clarity.	
5.	Addendum II	Removed duplicate variant in aMOI list (COSM180789)	
6.	Addendum III	Updated "Patient Drug Information Handout and Wallet Card" appendix with new language provided by CTEP	

The following revisions to EAY131-P Informed Consent Document have been made in this addendum:

	Section	Change	
1.	Page 1	Updated Version Date	

2.	"What are the study groups?"	Added additional dosing instructions for consistency with the subprotocol.
3.	"What are the study groups?"	The term "medication diary" has been replaced with the term "patient pill calendar" for consistency with the subprotocol.
4.	"What possible risks?	Updated contraception use from "continuing for up to 16 weeks" to "continuing for 16 weeks" as contraception is required for all 16 weeks after treatment.
5.	Study Calendar	The term "medication diary" has been replaced with the term "patient pill calendar" throughout for consistency with the subprotocol.

If you have any questions regarding this addendum, please contact [contact] or [contact].

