We request review and approval of this addendum to EAY131-P so ECOG-ACRIN may activate it promptly.

Thank you.

Sincerely,

[name]

Director of Protocol Development

Enclosure

CC: [name], PhD [name]

[name],

PhD

[name]

[name] [name] [name] [name] [name] [name] [name] [name] [name] [name]

[name] [name], PhD [name]

[name] [name] [name] [name] [name] [name] [name] [name] [name] [name] [name] [name], R.N. [name] [name] [name] [name] [name]

[name]

[name]

[name] [name]

Molecular Analysis for Therapy Choice (MATCH)

MATCH Treatment Subprotocol P: Phase II Study of PI3K Beta Specific Inhibitor, GSK2636771, in Patients with Tumors with PTEN Loss by IHC

GSK2636771 TREATMENT SUBPROTOCOL

CHAIR: [name], PhD

GSK2636771 TREATMENT SUBPROTOCOL

CO-CHAIR: [name]

GSK2636771 TRANSLATIONAL CHAIR: [name], PhD

Version Date: February 6, 2017

NOTE: This subprotocol (EAY131-P) should be used in conjunction with the MATCH

Master Protocol (EAY131).

SUBPROTOCOL ACTIVATION DATE

February 25, 2016 (Incorporated in Addendum #2)

Addendum #5 - 12/16 Addendum #7 - 3/17

Agent IND#		NSC#	Supply
GSK2636771	NCI Sponsor: DCTD, NCI IND #:	781258	NCI Supplied

Table of Contents

TREATMENT SUBPROTOCOL CHAIR

[name], PhD, The University of Texas **MD Anderson Cancer Center** The Department of Investigational Cancer Therapeutics (Phase I Clinical Trials Program) [name] [contact]

[contact]

Email: [contact]

TREATMENT SUBPROTOCOL CO-CHAIR

[name] The University of Pittsburgh Magee Womens Cancer Center [name] [contact] [contact]

Email: [contact]

[figure not shown]
TRANSLATIONAL CHAIR

[name], PhD Dana-Farber Cancer Institute Harvard Medical School Gynecologic Oncology Program [contact]

[contact]

Email: [name] [contact]

Schema

[figure not shown]
Cycle = 28 days Accrual Goal: 35

1. Introduction

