A History and physical, including vital signs and weight at the start of each cycle (up to 3 days before start of new cycle).

B. Albumin, alkaline phosphatase, total bilirubin, bicarbonate, BUN, calcium, creatinine, glucose, phosphorus, potassium, SGOT[AST], SGPT[ALT], sodium, magnesium and serum tumor markers (including LDH, PSA if appropriate). For eligibility purposes, participants with creatinine levels above institutional normal. Cockcroft-Gault will be used to calculate creatinine clearance. CBC w/diff. platelets and serum chemistries should be performed on cycle 1, day 1 (or up to 7 days prior), and at the start of each subsequent cycle (up to 3 days before start of new cycle). CBC with differential will be performed more frequently in patients with grade 4 neutropenia or thrombocytopenia until resolution to ≤ grade 3. CBC and serum chemistries are only required in follow-up until values return to pre-treatment levels or until progressive disease.

^{C.} Blood pregnancy test (women of childbearing potential) required prior to beginning treatment.

D. Disease measurements are repeated every 2 cycles for the first 26 cycles, and every 3 cycles thereafter until PD or start of another MATCH treatment step. The baseline evaluation should be performed as closely as possible to the beginning of treatment and never more than 6 weeks

before registration to treatment step. For multiple myeloma patients, please refer to Section 6.4 of the MATCH Master Protocol for additional information on myeloma response criteria and the required disease assessments. Documentation (radiologic) must be provided for patients removed from study for progressive disease.

- E. Additional blood specimens and/or biopsies are to be submitted from consenting patients per the MATCH Master Protocol. Submit at the following time points, as applicable:
 - Blood specimens are to be submitted at the end of Cycle 2 (prior to start of Cycle 3 treatment). If patient progresses or treatment is discontinued prior to Cycle 3, collect the blood at that time instead. See Section 9.3.2.3 of MATCH Master Protocol. On-treatment kits for blood sample collections will be automatically shipped to sites upon registration to the treatment step.
 - Screening biopsies for additional aMOI assessments after registration to appropriate screening step, if applicable (Step 2 or Step 4).
 - At end of all MATCH study treatments, blood specimens and/or research biopsy after consent and registration to Step 8

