Please refer to Section 4 of the MATCH Master Protocol to determine whether the patient proceeds to the next screening step or to follow-up (with a potential end of treatment biopsy for research purposes on Step 8). Samples are to be submitted as outlined in Section 9 of the MATCH Master Protocol. To order Step 2/4 Screening or Step 8 kits, complete the EAY131 Collection and Shipping Kit Order Form (See Appendix XII of the MATCH Master Protocol) and fax to [contact].

- F. Every 3 months if patient is < 2 years from study entry, and every 6 months for year 3. Toxicity assessments and radiologic evaluations are not required to be done during Follow Up if progression has been previously reported; however if an adverse event occurs post treatment that meets the SAE reporting requirements, it still must be reported via CTEP-AERS, even if progression has occurred.
- ^{G.} Site personnel should evaluate for toxicity and discuss treatment compliance with the patient in order to ensure the medication is taken correctly; this evaluation may be conducted by telephone or in person. The Toxicity Assessment is not required prior to Cycle 1, but is required every subsequent cycle.
- H. The pill calendar will be collected at the end of every cycle. The Pill Count/Diary is not required prior to Cycle 1, but is required every subsequent cycle.
- ^{1.} As clinically indicated.
- J. For Cycle 1, if the following tests/assessments occurred within 7 days of Day 1, they do not need to be repeated at this timepoint: H&P, Weight, Vital Signs; Performance Status; CBC w/diff, plts; Serum chemistry; Concomitant Medications.
- K. Within 8 weeks of treatment assignment.

5. Drug Formulation and Procurement

This information has been prepared by the ECOG-ACRIN Pharmacy and Nursing Committees.

Availability

NO STARTER SUPPLIES MAY BE ORDERED. Subjects must be enrolled and assigned to the treatment subprotocol prior to submitting the clinical drug request to PMB.

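### Does the 28-day pregnancy reporting window in section 3.2.1 conflict with the 16-week contraception requirement?

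*Protocol*

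**What the plan says.** Under the expedited reporting requirements in section 3.2.1, pregnancies, suspected pregnancies and positive or inconclusive tests "occurring while the subject is on GSK2636771 or within 28 days of the" subject's "last dose of GSK2636771, are considered immediately reportable events". The site has 24 hours from the investigator's knowledge to file through CTEP-AERS. The same bullet sends the site to Appendix VIII of the MATCH Master Protocol for how to report a pregnancy and the outcome of all pregnancies.

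Section 3.2 sets the frame: "The Adverse Event Reporting Requirements for all EAY131 subprotocols are outlined in the MATCH MASTER protocol". The agent-specific section applies in addition to those requirements.

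The 16 weeks appears in the Addendum #7 cover letter, in the list of consent document changes. The consent wording was made firmer, "as contraception is required for all 16 weeks after treatment". That is the new wording and the current requirement, so comparing it with section 3.2.1 is legitimate.

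Three other places bear on the point:

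- Section 4.1, footnote C: "Blood pregnancy test (women of childbearing potential) required prior to beginning treatment".
- Section 4.1, footnote F: "if an adverse event occurs post treatment that meets the SAE reporting requirements, it still must be reported via CTEP-AERS", even after progression.
- Schema: "Accrual Goal: 35".

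**The concern.** Two post-treatment periods that both concern pregnancy differ by a factor of four, and the protocol does not say why. If the drug calls for contraception for 16 weeks after treatment, a reader expects a pregnancy arising in those weeks to be of interest to the sponsor. Yet under section 3.2.1 alone, a pregnancy beginning on day 29 or later triggers no immediate report. Addendum #7 firmed up the contraception wording but did not list section 3.2.1 among the sections it revised, which suggests an oversight.

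Completeness of safety capture would be at stake. A site working only from the subprotocol might not report a late pregnancy that involved no serious adverse event or birth defect.

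**Working it through.** **1. The two periods.**

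- Contraception (cover letter): 16 weeks × 7 = 112 days.
- Reporting window (section 3.2.1): 28 days after the last dose, besides all time on drug.
- Difference: 112 − 28 = 84 days, or 12 weeks; 84/112 = 75%.

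This assumes that both periods start at the last dose. Section 3.2.1 counts from the last dose; the letter counts from the end of treatment.

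**2. Do the two rules contradict each other?** Set side by side:

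| | Contraception period | Section 3.2.1 window |
|---|---|---|
| Who must act | participant | site |
| What is required | avoid pregnancy | report within 24 hours |
| Post-treatment length | 16 weeks | 28 days |

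Complying with one never breaks the other. No sentence in the protocol says that the reporting window equals the contraception period or is derived from it. The lengths differ, but neither statement makes the other false.

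**3. Does the text show that late pregnancies go unreported?** It does not, for two reasons.

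- Section 3.2.1 is an addition to the Master Protocol's reporting rules and itself refers to Appendix VIII there. Whether those rules reach beyond 28 days cannot be read from the subprotocol.
- The consent form is not available, so it is unknown whether the 16 weeks binds women, men or both. Section 3.2.1 is written around the subject and the subject's last dose. If the 16 weeks applied to men only, there would be no 84-day gap for pregnancies in subjects. The animal findings do not settle this: section 1.2.4 reports spermatocyte depletion in rats and dogs, and section 3.3 lists ovarian cysts in rats.

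**4. Is 28 days visibly ill-chosen on the protocol's own figures?** Section 1.3.3 gives median half-lives from 17.1 to 38.6 hours over 25 to 500 mg once daily.

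- 28 days × 24 = 672 hours.
- 672 / 38.6 = 17.4 half-lives; 672 / 17.1 = 39.3 half-lives.

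This does not establish that 28 days is the right length. It shows only that the document's figures give no ground for calling the window badly fixed.

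**5. Upper bound on what could be missed.**

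- Person-time: 35 × 84 = 2,940 person-days; 2,940 / 365.25 = 8.05 person-years.
- The documents give no pregnancy rate. Assumed rates of 1, 5 and 10 per 100 person-years give 8.05 × 0.01 = 0.08, 8.05 × 0.05 = 0.40 and 8.05 × 0.10 = 0.805.

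The bound is generous, because it counts every patient as able to become pregnant. The arm evidently takes men as well: footnote B in section 4.1 lists PSA among the serum markers.

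**The case for a change.** The strongest case is practical. Section 3.2 tells sites that the agent-specific section must be followed for all reporting requirements to be met, and 28 days is the only window it shows. A site could take that as the whole rule. The study calendar lists pregnancy testing only before treatment, and follow-up visits come every 3 months in the first two years. A pregnancy may therefore first become known after day 28 and within the 16 weeks. Section 3.2.1 does not say how to treat a pregnancy conceived before day 28 but detected later, and it does not mention partner pregnancies. Section 1.2.4 reports effects on animal reproductive systems and describes no embryofetal study, so each exposed pregnancy carries information. A single explanatory sentence would cost almost nothing.

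Part of this stands. The difference is real, the arithmetic is right, and the subprotocol gives no explanation. Asking the sponsor to check the three documents together would be a fair query.

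The step from an unexplained difference to a defect does not stand. Explaining why two separate rules have separate lengths is helpful but not required for either to be correct. How a site handles late or partner pregnancies depends on the Master Protocol and the consent form, and their absence here is not a fault of the plan. The worst consequences also have their own route: footnote F keeps post-treatment events that meet serious adverse event requirements reportable, and section 3.2.1 separately directs sites on congenital anomalies and birth defects. What could remain is a late pregnancy with no such event, and then only if the Master Protocol does not cover it.

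**Conclusion.** The concern does not hold. The 28 days and the 16 weeks are both read correctly, and 84 days is the right difference if both run from the last dose. But they belong to different rules, addressed to different people, that can be followed together. The protocol contains no contradiction and no wrong figure here, and its own half-life data do not show the reporting window to be badly set.

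Whether any pregnancy would escape reporting cannot be determined without the Master Protocol and the consent form. If one did, the expected number would be below one: at most about 0.8, assuming 10 pregnancies per 100 person-years and all 35 patients able to become pregnant. Sample size, endpoints, analysis and error rates are unaffected. This conclusion takes no position on how long either period should be.

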3.2.2 Second Primary Cancer Reporting Requirements

All cases of second primary cancers, including acute myeloid leukemia (AML) and myelodysplastic syndrome (MDS), that occur following treatment on NCI-sponsored trials must be reported to ECOG-ACRIN using Medidata Rave

- A second malignancy is a cancer that is UNRELATED to any prior anti-cancer treatment (including the treatment on this protocol). Second malignancies require ONLY routine reporting as follows:
 - 1. Complete a Second Primary Form in Medidata Rave within 14 days.
 - 2. Upload a copy of the pathology report to ECOG-ACRIN via Medidata Rave confirming the diagnosis.
 - 3. If the patient has been diagnosed with AML/MDS, upload a copy of the cytogenetics report (if available) to ECOG-ACRIN via Medidata Rave.
- A secondary malignancy is a cancer CAUSED BY any prior anticancer treatment (including the treatment on this protocol).
 Secondary malignancies require both routine and expedited reporting as follows:
 - Complete a Second Primary Form in Medidata Rave within 14 days
 - 2. Report the diagnosis via CTEP-AERS at http://ctep.cancer.gov

Report under a.) leukemia secondary to oncology chemotherapy, b.) myelodysplastic syndrome, or c.) treatment related secondary malignancy

- 3. Upload a copy of the pathology report to ECOG-ACRIN via Medidata Rave and submit a copy to NCI/CTEP confirming the diagnosis.
- 4. If the patient has been diagnosed with AML/MDS, upload a copy of the cytogenetics report (if available) to ECOG-ACRIN via Medidata Rave and submit a copy to NCI/CTEP.

NOTE: The Second Primary Form and the CTEP-AERS report should not be used to report recurrence or development of metastatic disease.

NOTE: If a patient has been enrolled in more than one NCI-sponsored study, the Second Primary Form must be submitted for the most recent trial. ECOG-ACRIN must be provided with a copy of the form and the associated pathology report and cytogenetics report (if available) even if ECOG-ACRIN was not the patient's most recent trial.

3.3 Comprehensive Adverse Events and Potential Risks List (CAEPR) for GSK2636771 (NSC 781258)

The Comprehensive Adverse Event and Potential Risks list (CAEPR) provides a single list of reported and/or potential adverse events (AE) associated with an agent using a uniform presentation of events by body system. In addition to the comprehensive list, a subset, the Specific Protocol Exceptions to Expedited Reporting (SPEER), appears in a separate column and is identified with bold and italicized text. This subset of AEs (SPEER) is a list of events that are protocol specific exceptions to expedited reporting to NCI via CTEP-AERS (except as noted below). Refer to the 'CTEP, NCI Guidelines: Adverse Event Reporting Requirements'

http://ctep.cancer.gov/protocolDevelopment/electronic applications/docs/aeguide lines.pdf for further clarification. The CAEPR does not provide frequency data; refer to the Investigator's Brochure for this information. Below is the CAEPR for GSK2636771.

NOTE:

If an AE meets the reporting requirements of the protocol, and it is listed on the SPEER, it should ONLY be reported via CTEP-AERS if the grade being reported exceeds the grade listed in the parentheses next to the event in the SPEER.

Version 1.1, November 10, 2015¹

Adverse Events with Possible Relationship to GSK2636771 (CTCAE 4.0 Term)	Specific Protocol Exceptions to Expedited Reporting (SPEER)
GASTROINTESTINAL DISORDERS	
Abdominal pain	
Diarrhea	Diarrhea (Gr 2)
Nausea	Nausea (Gr 2)
Vomiting	Vomiting (Gr 2)
GENERAL DISORDERS AND ADMINISTRATION SITE CONDITIONS	
Fatigue	Fatigue (Gr 2)
INVESTIGATIONS	
Aspartate aminotransferase increased	
Creatinine increased	
METABOLISM AND NUTRITION DISORDERS	
Anorexia	Anorexia (Gr 2)
Hypocalcemia	
Hypophosphatemia	
NERVOUS SYSTEM DISORDERS	
Dysgeusia	
Headache	
SKIN AND SUBCUTANEOUS TISSUE DISORDERS	
Pruritus	
Rash maculo-papular	Rash maculo-papular (Gr 2)

¹This table will be updated as the toxicity profile of the agent is revised. Updates will be distributed to all Principal Investigators at the time of revision. The current version can be obtained by contacting

ECOG-ACRIN EAY131-P Version Date: February 6, 2017

[contact]. Your name, the name of the investigator, the protocol and the agent should be included in the e-mail.

Adverse events reported on GSK2636771 trials but for which there is insufficient evidence to suggest that there was a reasonable possibility that GSK2636771 caused the adverse event:

GASTROINTESTINAL DISORDERS - Constipation; Dry mouth; Mucositis oral; Small intestinal obstruction

GENERAL DISORDERS AND ADMINISTRATION SITE CONDITIONS - Fever; General disorders and administration site conditions - Other (mucosal inflammation); Pain

INFECTIONS AND INFESTATIONS - Upper respiratory infection

INVESTIGATIONS - Alanine aminotransferase increased; GGT increased; Investigations -Other (N-terminal prohormone brain natriuretic peptide increased); Neutrophil count decreased

METABOLISM AND NUTRITION DISORDERS - Hypoalbuminemia; Hypokalemia; Hypomagnesemia

PSYCHIATRIC DISORDERS - Depression; Insomnia

RENAL AND URINARY DISORDERS - Proteinuria; Urinary retention

RESPIRATORY, THORACIC AND MEDIASTINAL DISORDERS - Dyspnea; Productive cough **VASCULAR DISORDERS** - Hypertension

Animal Data: The following toxicities have been observed in animal studies with GSK2636771:

Dogs

HEPATOBILIARY DISORDERS - Single cell hepatocellular necrosis with perivascular mixed inflammatory cell infiltrate; pigmented macrophages and kupffer cells

IMMUNE SYSTEM DISORDERS - Lymphoid necrosis (spleen, lymph node, GALT)

INVESTIGATIONS - Increased glutamate dehydrogenase (GLDH)

RENAL AND URINARY DISORDERS - Tubular degeneration/regeneration

REPRODUCTIVE SYSTEM AND BREAST DISORDERS - Seminiferous tubular depletion

Rats

BLOOD AND LYMPHATIC SYSTEM DISORDERS - Leukocytosis

GASTROINTESTINAL DISORDERS - Focal erosions and/or erosion/ulcer and mucous cell hypertrophy in glandular region

IMMUNE SYSTEM DISORDERS - Decreased thymus weight

INVESTIGATIONS - Increased serum urea; weight loss

RENAL AND URINARY DISORDERS - Hyaline droplets in cortical proximal tubule; increased kidney weight; increased urinary biomarkers; inflammatory cell infiltrate in cortex; necrosis of cortical tubules: tubular basophilia

REPRODUCTIVE SYSTEM AND BREAST DISORDERS - Decreased testis weight; reddened ovarian cysts; spermatid retention; spermatocyte depletion

NOTE: GSK2636771 in combination with other agents could cause an exacerbation of any adverse event currently known to be caused by the other agent, or the combination may result in events never previously associated with either agent.

EAY131-P Version Date: February 6, 2017

Rev. 12/16 3.4 **Dose Modifications**

All toxicity grades below are described using the NCI Common Terminology Criteria for Adverse Events (CTCAE) version 4.0.

All appropriate treatment areas should have access to a copy of the CTCAE version 4.0. A copy of the CTCAE version 4.0 can be downloaded from the CTEP website (http://ctep.cancer.gov).

GSK2636771 will be administered on an oral, daily, continuous administration schedule. The starting dose of the drug will be 400mg (four 100 mg capsules), once daily which was deemed the maximum tolerated phase II dose from the company sponsored phase I study.

Each cycle of therapy will be 28 days and there will not be any scheduled breaks between dosing cycles. Patients must meet the following criteria in order to proceed with the next cycle of treatment:

- ANC ≥ 1,000/µL
- Platelets ≥ 75,000/µL
- Hemoglobin ≥ 9 g/dL
- Phosphorous, magnesium, potassium, and calcium (corrected for albumin) must either be within normal range for labs or no worse than grade 2. Supplementations may be used to keep within these ranges.
- Serum creatinine must be ≤ 1.5 x ULN or 24-hour creatinine clearance of \geq 50 mL/min.

At the beginning of a cycle, patients experiencing any toxicity that meets definition of grade 3 or 4 toxicity will have the study drug held until resolution of symptoms to grade 1 or baseline, unless otherwise specified in the protocol. Within cycle toxicity that meets grade 3 or 4 criteria, will necessitate holding of the drug until the toxicity are improved to grade 1 or baseline, unless otherwise specified in the protocol. In general, except as directed for specific examples in the following tables, if there is need to interrupt dosing for grade 3/4 toxicity, then there will be a dose reduction as per the table below, once toxicity improved to grade 1 or baseline. Dose may be suspended for up to 2 weeks due to toxicity. If treatment held for laboratory abnormality; recheck labs in one week. GSK2636771 will not be re-escalated once dose reduced.

For diarrhea, nausea and vomiting, optimal supportive care should be initiated prior to dose reduction. If symptoms persist despite maximal supportive care, or at investigator discretion, doses may be reduced per criteria below. Suspend GSK2636771 for grade 3 or 4 symptoms and hold until resolved to grade 1 or baseline, unless otherwise specified in the protocol.

Dose Reduction Table:

Dose levels and dose reductions:	GSK2636771 dose	
Starting dose level	400 mg po daily	
Dose level -1	300 mg po daily	
Dose level -2	200 mg po daily	

Renal Insufficiency/ Creatinine Increased:

Toxicity grade	Action	Dose modification	Subsequent occurrences
Grade 1	Continue with current dose	none	none
Grade 2	Hold until grade 1	Reduce one dose level	2nd occurrence: reduce additional dose level 3 rd occurrence: discontinue GSK2636771
Grade 3	Hold until grade 1	Reduce one dose level	2nd occurrence: reduce additional dose level 3 rd occurrence: discontinue GSK2636771
Grade 4	Hold until grade 1	Reduce two dose levels	2 nd occurrence: discontinue GSK2636771

Neutropenia:

Toxicity grade	Action	Dose modification	Subsequent occurrences
Grade 1 or 2	None	Maintain current dose level	
Grade 3	Hold GSK2636771 until grade 2	None	Reduce one dose level
Grade 4	Hold GSK2636771 until grade 2	Reduce one dose level	Reduce one dose level

Thrombocytopenia:

Toxicity grade	Action	Dose Modification	Subsequent Occurrences
Grade 1	None	Maintain current dose level	None
Grade 2	Hold until grade 1	Maintain current dose level	Reduce one dose level
Grade 3	Hold until grade 1	Reduce one dose level	Reduce one dose level
Grade 4	Hold until grade 1	Reduce one dose level	Reduce one dose level

Liver Function Tests (bilirubin, AST and ALT):

Toxicity grade	Action	Dose modification	Subsequent occurrences
Grade 1	None	Maintain current dose level	
Grade 2	None	Maintain current dose level	
Grade 3	Hold until grade 1	Reduce one dose level	Reduce one dose level
Grade 4	Hold until grade 1	Reduce one dose level	Reduce one dose level

Rev. 12/16 **Hypophosphatemia**:

Toxicity grade	Action	Dose modification	Subsequent occurrences
Grade 1: < LLN-2.5 mg/dL	Continue with current dose	None	None
Grade 2: < 2.5-2.0 mg/dL	Replace phosphorous per institutional guidelines	Maintain current dose level	2nd occurrence: reduce additional dose level 3rd occurrence: discontinue GSK2636771
Grade 3: < 2.0-1.0 mg/dL	Replace phosphorous per institutional guidelines, hold until grade 1	Reduce one dose level	2nd occurrence: reduce additional dose level 3rd occurrence: discontinue GSK2636771
Grade 4: < 1.0 mg/dL	Replace phosphorous per institutional guidelines, hold until grade 1	Reduce one dose level	2nd occurrence: reduce additional dose level 3rd occurrence: discontinue GSK2636771

